7.2 Clinical Laboratory Analyses

All clinical laboratory values will be listed individually and tabulated in a manner to identify safety concerns on a per-patient basis. Listing tables will be prepared for each laboratory measure and will be structured to permit review of the patient data as they progress on treatment. The tables will list the cycle of treatment, BXCL701 dose for Lead-in data, and the associated NCI CTCAE grade. Descriptive summary statistics will be generated per laboratory parameter.

Summary tables will be prepared to examine the distribution of these toxicities per cycle.

Graphic displays and shift tables may be provided to illustrate results over time on study. Assessment of cumulative toxicities may be made.

8 INVESTIGATOR REQUIREMENTS

8.1 Protocol Adherence

Each investigator must adhere to the protocol as detailed in this document and agree that any intended departures from the protocol must be approved by the Principal Investigator or her/his designee prior to seeking approval from the IRB. Each investigator will be responsible for enrolling only those patients who have met protocol eligibility criteria.

8.2 Study Monitoring Requirements

Site visits will be conducted by the sponsor or sponsor's representative to inspect study data, patients' medical records, and other documents in accordance with current Food and Drug Administration (FDA) Good Clinical Practices (GCP), the International Council for Harmonisation (ICH) guidelines, and the respective local and national government regulations and guidelines. The investigator will permit the sponsor and/or authorized representatives of the sponsor, the FDA, and the respective national or local health authorities to inspect his or her facility and records relevant to this study.

8.3 Drug Accountability

Inventory control of all BXCL701 must be maintained throughout the duration of the study. Any discrepancies that are noted between drug-dispensing records and drug inventory must be reported. Medication-dispensing records are provided to the investigative site. All study medication used during the study must be accounted for on the appropriate form. All unused study medication must be returned by the patient to the site for completion of their drug accountability record. All unused study medication will be disposed of in biohazard containers in accordance with the policies of the institution by site personnel.

8.4 Retention of Records

Records and documents pertaining to the conduct of this study, including screening logs, source documents, consent forms, laboratory test results, medication inventory records and other documents must be retained according to the local standard operating procedures and institutional and/or IRB policies.

8.5 Study Discontinuation

A discontinuation occurs when an enrolled patient ceases participation in the study, regardless of the circumstances, prior to completion of the protocol. The investigator must determine the primary reason for discontinuation. The investigator or study coordinator must notify the supporting company immediately when a subject/patient has been discontinued/ withdrawn due to an adverse experience (telephone or FAX). When a subject/patient discontinues/withdraws prior to study completion, all applicable activities scheduled for the final study visit should be performed at the time of discontinuation.

8.5.1 Discontinuation/Withdrawal Criteria

- A patient may be withdrawn by the investigator or the supporting company if he/she violates the study plan or for administrative and/or other safety reasons.
- The patient withdraws consent at any time after agent administration. Every effort will be made to determine why any subject withdraws from the study prematurely.

- The patient is lost to follow-up. A genuine effort must be made to determine the reason(s) why a patient fails to return for the necessary visits. If the subject is unreachable by telephone, a registered letter, at the minimum, should be sent requesting him/her to contact the clinic.
- Disease progression. RECIST 1.1 and iRECIST will be used for assessment of tumor response for the purposes of managing patients on protocol treatment and decision making for discontinuation of study therapy due to disease progression. Response assessments with CT and/or MRI will be done every 9 weeks (3 cycles) following RECIST and iRECIST criteria (intervals can be shortened to 6 weeks if clinically necessary per treating physician). Patients with disease progression per RECIST and/or iRECIST can continue on therapy for clinical benefit if deemed appropriate by the investigator.
- The patient starts a new anti-cancer therapy
- There is a need for any treatment not allowed by the protocol
- Any life-threatening AE.

Any adverse experiences that are present at the time of discontinuation/withdrawal should be followed in accordance with the safety requirements outlined in Section 5.3 Safety Assessments.

Patients who discontinue study treatment who have not shown disease progression and have not withdrawn consent will continue to be followed for disease progression and survival.

9 ETHICAL CONSIDERATIONS

This study will be conducted in accordance with current FDA regulations, GCP, the ICH guidelines, the ethical principles that have their origins in the Declaration of Helsinki, and local ethical and legal requirements.

ADT	Androgen deprivation therapy
AE	Adverse event
ALT	Alanine aminotransferase
ANC	Absolute neutrophil count
AR	Androgen receptor
AST	Aspartate aminotransferase
AUC	Area under the plasma concentration-time curve
AUC _{0-last}	Area under the plasma concentration time curve for the last measurable concentration
BID	Twice daily
BS	Bone scintigraphy
BUN	Blood urea nitrogen
С	Cycle
Са	Calcium
CAF	Cancer associated fibroblast
CI	Confidence interval
Cl	Chloride
CLL	Chronic lymphocytic leukemia
C _{max}	Maximum plasma concentration
CNS	Central nervous system
CR	Complete response
Cr	Creatinine
CRPC	Castration-resistant prostate cancer
СТ	Computed tomography
CTC	Circulating tumor cells
ctDNA	Circulating tumor DNA
CTLA-4	Cytotoxic T-lymphocyte-associated antigen 4
СҮР	Cytochrome P450
D	Day
DKA	Diabetic ketoacidosis
DLT	Dose-limiting toxicity
DOR	Duration of response
DPP	Dipeptidyl peptidase
DSRC	Data Safety Review Committee
ECOG	Eastern Cooperative Oncology Group
eCRF	Electronic case report form
EOT	End of Treatment
FAP	Fibroblast activation protein

10 LIST OF ABBREVIATIONS

FDA	Food and Drug Administration
GCP	Good Clinical Practice
G-CSF	Granulocyte-colony stimulating factor
IC ₅₀	Half maximal inhibitory concentration
ICH	International Council for Harmonisation
IEC	Independent Ethics Committee
IL	Interleukin
IND	Investigational New Drug (Application)
IRB	Institutional Review Board
iRECIST	Immune Response Evaluation Criteria In Solid Tumors
ITT	Intent-to-Treat
IV	Intravenous
K	Potassium
LDH	Lactate dehydrogenase
LHRH	Luteinizing hormone-releasing hormone
MDSC	Myeloid derived suppressor cell
MedDRA	Medical Dictionary for Regulatory Activities
Mg	Magnesium
MRI	Magnetic resonance imaging
mRNA	Messenger ribonucleic acid
Na	Sodium
NCI CTCAE	National Cancer Institute Common Terminology Criteria for Adverse Events
NEPC	Neuroendocrine prostate cancer
NHL	Non-Hodgkin's lymphoma
NSCLC	Non-small cell lung cancer
OS	Overall survival
PCWG3	Prostate Cancer Working Group 3
PD	Progressive disease
-	
PD-1	Programmed cell death 1
PD-1 PD-L1	-
	Programmed cell death 1
PD-L1	Programmed cell death 1 Programmed death-ligand 1 Programmed death-ligand 2
PD-L1 PD-L2	Programmed cell death 1 Programmed death-ligand 1
PD-L1 PD-L2 PFS	Programmed cell death 1 Programmed death-ligand 1 Programmed death-ligand 2 Progression-free survival
PD-L1 PD-L2 PFS PR	Programmed cell death 1 Programmed death-ligand 1 Programmed death-ligand 2 Progression-free survival Partial response
PD-L1 PD-L2 PFS PR QTcB	Programmed cell death 1 Programmed death-ligand 1 Programmed death-ligand 2 Progression-free survival Partial response QT interval corrected for heart rate using Bazett's formula
PD-L1 PD-L2 PFS PR QTcB RECIST	Programmed cell death 1Programmed death-ligand 1Programmed death-ligand 2Progression-free survivalPartial responseQT interval corrected for heart rate using Bazett's formulaResponse Evaluation Criteria In Solid Tumors
PD-L1 PD-L2 PFS PR QTcB RECIST rPFS	Programmed cell death 1Programmed death-ligand 1Programmed death-ligand 2Progression-free survivalPartial responseQT interval corrected for heart rate using Bazett's formulaResponse Evaluation Criteria In Solid TumorsRadiographic progression-free survival

SJS	Stevens-Johnson syndrome
TEN	Toxic epidermal necrolysis
T1DM	Type 1 diabetes mellitus
t _{max}	Time of maximum observed concentration
ULN	Upper limit of normal
US	United States

12 APPENDIX A: STUDY SCHEDULE OF ASSESSMENTS

Screen Period			Cycle 1						Cycle	2			>C	ycle 2		EOT Visit ^a	FU Visit ^b	
Screen/Cycle Day (D):	D-28 to D-1	D1 ⁱ	D2	D5 ^t	D8 ^r	D14	D15 ^r	D1°	D2	D8 ^r	D14	D15 r	D1°	D8	D14	D15		
Informed consent	X																	
Inclusion and exclusion criteria	X	Х																
Demographics	X																	
Adverse Event Assessment	X	Х	Х	X	X		Х	Х		Х		Х	Х				Х	Х
Concomitant Medications	X	Х	Х	X	X		Х	Х		Х		Х	Х				Х	Х
cancer treatment history	X																	
Archival tumor collection ¹	X																	
Imaging and Other																		
CT/MRI	X												X ^d				X ^d	
Tumor assessment	X												X ^d				X ^d	
Study Drug Administration																		
BXCL701 administration				Day	1-14				Day	1-14			D	ay 1-	14			
Ambulatory monitoring of blood pressure before each dose of BXCL701				Day	1-14			Day 1-14					Day 1-14					
Oral hydration monitoring				Day	1-14			Day 1-14					D	ay 1-	14			
Daily safety telephone calls			Da	y 3-4,	Day 6	-14												
Pembrolizumab administration ^j		Х						Х					Х					
Clinical Procedures																		
Physical examination	X	Х	Х	Х	X		Х	Х		Х		Х	Х				Х	
Medical history/current medical conditions	X	Х	Х	Х	Х		Х	Х		Х		Х	Х				Х	
ECOG performance status	Х	Х	Х	Х	Х		Х	Х		Х		Х	Х				Х	

	Screen Period		(Cycle	1		Cycle	2			>C	ycle 2	EOT Visit ^a	FU Visit ^b				
Screen/Cycle Day (D):	D-28 to D-1	D1 ⁱ	D2	D5 ^t	D8 ^r	D14	D15 ^r	D1°	D2	D8 ^r	D14	D15 r	D1 ^c	D8	D14	D15		
Vital signs (BP, HR, body temperature, RR, O2 saturation)	X	Х	X	X	X		X	Х		Х		Х	Х				Х	
Height	Х	Х	Х	Х	Х		Х	Х		Х		Х	Х				Х	
Weight	X	Х	Х	Х	Х		Х	Х		Х		Х	Х				Х	
Clinical Laboratory Tests ^q																		
Hematology (CBC plus differential [5-part or auto- analyzer])	X	Х			X		Х	Х		X		Х	Х	X ^v		Xv	Х	
Serum chemistry ^e	Х	Х			Х		Х	Х		Х		Х	Х	Xv		Xv	Х	
Liver function tests ^f	X	Х			X		Х	Х		Х		Х	Х	Xv		Xv	Х	
T3, FT4, TSH	Xu												Xu				Xu	
Cytokine-12 panel		Х	Х	Х														
Urinalysis	Х	Х						Х					Х				Х	
Serum collection ^g		Х	Х			Х	Х	Х	Х			Х						
Whole blood collection for immune parameters ^k		Х					Х	Х				Х					Х	
Tumor biopsies ^m	X ^m									X ^m							X ^m	
Blood collection for ctDNA ^s		X ^h	X ^h		X ^h		Х	\mathbf{X}^{h}					X ^h				Х	
Pregnancy test	X ⁿ	X ^{o,p}						X°					Xº					

Abbreviations: BP = blood pressure; CxDx = Cycle (number) Day (number); CBC = complete blood count; CT = computed tomography; ECOG = Eastern Cooperative Oncology Group; EOT = End of Treatment; FU = follow-up; HR = heart rate; MRI = magnetic resonance imaging; RR = respiratory rate.

a. After discontinuation of study drugs, patients will complete an EOT visit within 21 days after the last study drug dose.

Protocol 2019-0748 08 Apr 2022

- b. A Safety Follow-up Visit is to be conducted 30 days (±7 days) after the last dose of study drug and later if drug-related AEs have not resolved at that time. Thereafter, patients without documented disease progression (PD) will be followed every 90 days for disease assessments until documentation of PD. After documentation of PD, patients will be followed every 90 days for survival status; such follow-up will likely be conducted by telephone.
- c. Day 1 of Cycle 2 and all subsequent cycles will be 21 days (± 3 days) after the previous dose of study drug was administered.
- d. Tumor assessment must include cross-sectional imaging (MRI or CT scanning with intravenous contrast whenever possible) of the chest/abdomen/pelvis plus whole-body bone scan. Other body sites (e.g., neck) to be included as clinically indicated. Tumor assessment to be performed at Screening, C4D1 (±7 days), C7D1 (±7 days), C10D1 (±7 days), and Day 1 (±7 days) of every 3rd cycle thereafter and at EOT. Intervals for scans can be shortened to 6 weeks (e.g. C3D1, C5D1 etc.) if clinically necessary per treating physician.
- e. Serum chemistry to include: sodium (Na), potassium (K), chloride (Cl), bicarbonate, calcium (Ca), magnesium (Mg), phosphate, blood urea nitrogen (BUN)/creatinine (Cr), and lactate dehydrogenase (LDH).
- f. Liver function tests include aspartate aminotransferase, alanine aminotransferase, alkaline phosphatase, total bilirubin, and albumin.
- g. Serum will be collected if feasible predose (within 1 hour ± 30 minutes) and then 6 hours (± 1 hour) and 24 hours (±3 hours) postdose on C1D1. It will be also collected on C1D14 (± 1 days) and C2D1 (± 1 day) with the same daily schedule as C1D1 (pre-dose, 6 and 24 hours post-dose). The C1D1 and C2D1 24-hour samples will be collected prior to the D2 doses. C1D14 24-hour samples will be collected on C1D15. There will not be predose or 6-hour postdose serum collection on C2D14. Instead, there will be only one time 24-hour postdose collection on C2D15. Details about collection and processing are in the Laboratory Manual.
- h. Samples should be collected before dosing.
- i. If Cycle 1 Day 1 occurs <72 hours after Screening, physical examinations and clinical laboratory tests do not need to be repeated.
- j. Either BXCL701 or pembrolizumab may be administered first. However, on Cycle 1 Day 1, it is recommended that pembrolizumab will be administered first and that ≥1 hour should elapse before the administration of BXCL701 so that it will be easier to determine the relatedness of any AEs to study drug. It is s recommended to administer at least 1L of IV fluids if not medically contraindicated at Cycle 1 Day 1. It is at the investigator's discretion to provide IV hydration during in-person clinic visits beyond Cycle 1 Day 1.
- k. Whole blood will be collected on C1D1, C1D15 (±1 day), C2D1, C2D15 (±1 day), and at EOT for assessment of leukocytes by flow cytometry and other studies. Details about collection and processing are in the Laboratory Manual.
- 1. Archival tissue will be collected if available. Details about collection and processing are in the Laboratory Manual.
- m. Optional tumor biopsies will be obtained during screening and between Day 8 and Day 14 of cycle 2, and at EOT. Pre and post treatment biopsies will be mandatory if medically feasible in cohorts advancing to BOP2 stage. Details about collection and processing are in the Laboratory Manual.

Protocol 2019-0748 08 Apr 2022

- n. Pregnancy tests will be only for women with child bearing potential. Only whole blood will be collected for the pregnancy test that will be performed in the screening period (D -28 to D -1)
- o. Additional pregnancy tests will be performed D1 of each cycle only for women with child bearing potential. Whole blood or urine can be collected for the test.
- p. Pregnancy test for the D1 of the 1st cycle can be skipped if the test for the screening period is performed close to the 1st cycle.
- q. Laboratory assessment for immune-related toxicities will be added as per patient's toxicity and as needed upon the investigator's discretion.
- r. Days 8 and 15 of Cycles 1 and 2 can have a window of \pm 2 days. These visits can be also preformed using the telehealth in case of unanticipated events such as COVID-19 pandemics if in agreement with applicable regulations.
- s. Details about collection and processing are in the Laboratory Manual.
- t. C1D5 visit has a window of -1 day and can happen on C1D4.
- u. T3, FT4 and TSH testing will performed at baseline, C4D1 (±7 days), C7D1 (±7 days), C10D1 (±7 days), and Day 1 (±7 days) of every 3rd cycle thereafter and at EOT.
- v. Hematology (CBC plus differential [5 part or auto-analyzer]), serum chemistry and liver function tests will not be performed on Days 8 and 15 after Cycle 4 (at Cycle 5 and beyond)

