In both Lead-in and Efficacy Stages, patients will be screened for study eligibility within 28 days before the first study drug dose after provision of written informed consent. Patients who are determined to be eligible, based on Screening assessments, will be enrolled in the study on Cycle (C)1, Day (D)1 (Baseline, before the first dose of BXCL701).

During treatment, patients will attend study center visits and have study evaluations performed as detailed in the Schedule of Assessments (Appendix A). All study visits will

be conducted on an outpatient basis but may be conducted on an inpatient basis per the investigator's judgement.

All patients must have pre-treatment (prior to study treatment dosing) imaging (computed tomography [CT] scan of chest/abdomen/pelvis or magnetic resonance imaging [MRI] for baseline tumor measurements, as well as bone scintigraphy [BS, if deemed necessary]). Patients with skin, subcutaneous or lymph node metastases may also have tumor evaluations (including measurements, with a ruler) by means of physical examination. Patients with a history of central nervous system (CNS) malignant involvement or CNS symptoms should have either CT or MRI imaging of the brain performed to assess active CNS malignancy.

Tumor measurements and disease response assessments (CT or MRI; BS) are also to be performed at the end of Cycle 3 (approximately 9 weeks after the first study treatment dose), and then approximately every 9 weeks thereafter until development of progressive disease (PD). Intervals can be shortened to 6 weeks if clinically necessary per treating physician. For patients with evidence of disease control (stable disease or better) at Week 27, tumor measurements and disease response assessments may be performed less frequently (approximately every 12 weeks) thereafter. Tumor measurements and disease response assessments also are to be performed at the End of Treatment (EOT) visit.

Study procedures are listed in Appendix A.

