- A maximum of 2 dose reductions per participant will be permitted for BXCL701-related AEs, after which the study drug will be permanently discontinued.
- Adverse events deemed related to BXCL701 not recovering to ≤ Grade 1 or baseline within 6 weeks from onset will require permanent discontinuation of BXCL701.
- Discontinue BXCL701 for any life-threatening AE.

If an SAE thought to be related to BXCL701 occurs during the Treatment Period, dosing of BXCL701 should be interrupted in that patient until the SAE resolves. If the Investigator wishes to continue the patient on BXCL701, the supporter should be contacted to discuss continuing BXCL701 at the same or reduced dose.

If BXCL701 is discontinued due to an AE, all termination from treatment procedures and assessments must be performed.

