6.5 Pembrolizumab Administration, Dose Modifications and Discontinuation

Pembrolizumab will be prepared, stored, and administered according to the current full Prescribing Information. Pembrolizumab will be obtained from commercial supplies and will be administered 200 mg intravenously over 30 minutes through a 0.2 to 5 micron sterile, nonpyrogenic, low-protein binding online or add-on filter. No other medication will be infused through the infusion line. Infusion will be interrupted and slowed for grade 1 or 2 infusion-related reactions and permanently discontinued for grade 3 or 4 infusion-related reactions. Pembrolizumab will be administered until disease progression, unacceptable toxicity, or withdrawal of consent.

AEs associated with pembrolizumab exposure may be immune-mediated. Immune-related AEs may occur any time after pembrolizumab administration and may affect multiple body systems. Early recognition and treatment are important to reduce complications. Most immune-related AEs are reversible and can be managed with discontinuation of pembrolizumab and initiation of steroids. Refer to the current regional pembrolizumab full Prescribing Information for recommended dose modifications for the management of toxicities (including immune-mediated reactions and infusion-related reactions) considered related to pembrolizumab. Patients who require a dose hold of pembrolizumab of \geq 42 days will be discontinued from the study.

Pembrolizumab should not be used in conjunction with other immunosuppressive agents other than corticosteroids administered for control of immune reactions considered related to pembrolizumab. Refer to the current regional pembrolizumab full Prescribing Information for further details.

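### Patients who stop treatment without progression move from scans about every 9 weeks (Section 3) to every 90 days (Appendix A note b), so their progression is recorded later

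*Combined protocol and SAP*

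**What the plan says.** Section 3 (Study Design) places the first on-study scan "at the end of Cycle 3 (approximately 9 weeks after the first study treatment dose), and then approximately every 9 weeks thereafter", continuing until progression. For patients with disease control at Week 27, assessments "may be performed less frequently (approximately every 12 weeks) thereafter". A scan is also required at the End of Treatment (EOT) visit. Nothing in Section 3 limits the schedule to patients still on drug.

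Appendix A sets the timing differently. Note d reads "Tumor assessment to be performed at Screening, C4D1" and goes on to C7D1, C10D1 and every third cycle, each with a 7-day margin, plus EOT. Note c dates each Day 1 at 21 (± 3) days after the previous dose of study drug. Note a puts the EOT visit within 21 days of the last dose. Note b sets a safety visit 30 days after the last dose, and then: "Thereafter, patients without documented disease progression (PD) will be followed every 90 days for disease assessments until documentation of PD".

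Two other sections bear on follow-up. Section 6.5 says that patients who need a pembrolizumab hold of at least "42 days will be discontinued from the study". Section 8.5.1 says that patients who stop study treatment "who have not shown disease progression and have not withdrawn consent will continue to be followed for disease progression and survival", but gives no interval.

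**The concern.** PFS and duration of response are secondary objectives (Section 2.2), and both end on the date a scan shows progression. Section 13.4 ends response duration at the first objectively documented progression. If the scan interval widens when treatment stops, the recorded date depends on treatment status as well as on the disease. A patient who stops without progression for any reason, toxicity included, is looked at less often and appears progression-free for longer. The plan gives no PFS censoring or missed-scan rule that would limit this.

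There is a second, smaller issue. The response decision rests on a single unconfirmed scan (Section 7), and the first efficacy review follows 9 weeks of treatment. A patient who stops early may have no scheduled scan near week 9, so a response could be found late or missed.

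**Working it through.** The plan states no figure for scan timing, so there is none to reproduce. Days below are counted from the first dose.

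**1. Scan dates after stopping.** Inputs: 63-day interval, or 84 days after Week 27 (Section 3); EOT scan by last dose + 21 (note a); safety visit at last dose + 30, then 90 days (note b). Note b does not state the origin of the 90 days, so the first off-treatment scan is at last dose + 90, or at last dose + 30 + 90 = last dose + 120.

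| Last dose | EOT scan by | Next scan, Section 3 | Next scan, note b |
|---|---|---|---|
| day 21 | day 42 | day 63 | day 111 or 141 |
| day 42 | day 63 | day 126 | day 132 or 162 |

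The gap after an EOT scan at 21 days is 90 − 21 = 69 or 120 − 21 = 99 days.

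**2. Mean delay from true progression to the scan that shows it.** Assume exponential progression times with median m, so λ = ln 2 / m, and progression after the EOT scan. If the first gap is g₁ and later gaps are g, then

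mean delay = g₁ + g·exp(−λg₁) / (1 − exp(−λg)) − 1/λ.

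Example with m = 90 and last dose on day 21 (1/λ = 129.8):
- Section 3 at 9 weeks, g₁ = 21, g = 63: 21 + 63 × 0.851/0.384 − 129.8 ≈ 30.6 days.
- Note b counted from last dose, g₁ = 69, g = 90: 69 + 90 × 0.588/0.5 − 129.8 ≈ 45.0 days.
- Note b counted from the safety visit, g₁ = 99, g = 90: 99 + 90 × 0.467/0.5 − 129.8 ≈ 53.1 days.

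Over m = 90, 120 and 180 and last dose on day 21 or 42 (the 12-week option uses the same sum, with gaps changing from 63 to 84 days after day 189):

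| Schedule | Mean delay (days) |
|---|---|
| Section 3, 9-weekly throughout | 30.6 to 34.0 |
| Section 3, 12-weekly after Week 27 | 34.6 to 39.8 |
| Note b, from last dose | 44.9 to 45.0 |
| Note b, from safety visit | 49.2 to 53.1 |

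Case by case, note b adds:
- from the safety visit: 16 to 23 days against 9-weekly scans, and 9 to 19 days if the 12-week option is used;
- from the last dose: 11 to 14 days and 5 to 10 days respectively.

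The overall range is about 5 to 23 days. These are averages. A single progression can be caught earlier under note b if it falls just before a note b scan.

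**3. Effect on a cohort mean.** The documents do not give the share of patients who stop without progression. If it were 10% to 30% (assumed), the cohort mean would move by 0.10 × 5 = 0.5 to 0.30 × 23 ≈ 7 days.

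**4. Delayed cycles.** C4D1 is nominally 3 × 21 = 63 days after first dose. Under Section 6.5 a pembrolizumab hold must stay under 42 days for the patient to remain on study. One 41-day delay gives 63 + 41 = day 104.

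**5. Week-9 scan.** With the 7-day margin the window is days 56 to 70. The EOT scan falls by last dose + 21, so it must precede day 56 if the last dose is before day 35. The next note b scan is at least 90 days after the last dose, hence after day 70. Such a patient has an EOT scan but no scheduled scan in the window.

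**The case against.** The best defence is that there are two phases and no conflict. Section 5.2 describes 9-weekly assessment during treatment, so note d may be the on-treatment schedule and note b the intended off-treatment one. That reading is possible, but Section 3 does not say it, and it would leave the interval dependent on treatment status.

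Other points on that side stand:
- Section 3 is not a pure calendar rule. It is anchored to the end of Cycle 3 and agrees with note d whenever cycles run on time. They part only when Day 1 slips.
- A hold of BXCL701 alone need not move Day 1, since Section 6.2 says held doses are not made up.
- After Week 27 the contrast can be small: 84 against 90 days.
- The EOT scan means that early stoppers do have a post-baseline assessment.

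A reader might go further than the documents allow. Section 6.2 says that when BXCL701 is stopped for an adverse event "all termination from treatment procedures and assessments must be performed", which could suggest that a patient still on pembrolizumab drops to 90-day scans. Note a, however, speaks of stopping study drugs in the plural, and nothing places such a patient under note b. A reader might also infer that a patient who stops in Cycle 1 has no scan near week 18. With a last dose on days 0 to 13, counting from the safety visit gives days 120 to 133, within 7 days of day 126. Finally, the wider interval is not confined to toxicity: note b covers any stop without progression.

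**Conclusion.** The point holds as a bias in absolute estimates. Patients who stop without progression have later progression recorded about 5 to 23 days later on average than under Section 3. This assumes exponential progression with a median of 90 to 180 days and progression after an EOT scan at 21 days. The spread comes mainly from the unstated origin of the 90 days and from whether the 12-week option is used. PFS and duration of response are biased upward. The cohorts are single-arm with at most 17 evaluable patients each, so this is not a between-arm bias, and the shift in a cohort mean is smaller in proportion to the share who stop this way.

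It is tempting to infer a loss of power for the primary endpoint. The documents do not support a figure. They set no time window for response, so a later scan can still count. They do not define evaluability for patients who stop before 9 weeks, and they give no share of responses that would be missed. A late or missed response is possible but cannot be quantified. The finding merits an amendment; it does not undermine the design.

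**What to change.** - **Note d:** state scan times as weeks from first dose (9, 18, 27, then the Section 3 interval), regardless of holds or cycle delays.
- **Note b:** replace the 90-day disease assessments with the same Section 3 schedule for patients off treatment without progression. Continue until progression, start of new anticancer therapy, withdrawal of consent or death. Keep 90 days for survival contacts only. Naming new anticancer therapy as an end point for scans avoids crediting this regimen with the effect of a later one.
- **Sections 3 and 5.2:** make them say the same about patients off treatment.
- **Sections 6.5 and 8.5.1:** reconcile removal from the study after a long pembrolizumab hold with the continued follow-up of patients who have not progressed.

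The cost is amendment wording and a few more or earlier scans for patients off treatment, at an interval Section 3 already states.
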